### **5.2.2.2 Secondary efficacy analyses**

A large block of text has been completely redacted with black bars.

### **5.2.2.3 Sub-group analyses**

Preplanned sub-group analyses will be performed for the primary analysis variables on the following variables:

- Country
- Wound duration at inclusion (<5 months; ≥5 months)
- Wound area at inclusion (<10 cm^2; ≥10 cm^2)

Additional explorative sub-group analyses will be defined in SAP.

#### **5.2.2.4 *Interim analysis***

Interim analyses will only be performed by the IARC group.

#### **5.2.2.5 *Statistical Analysis Plan (SAP)***

A Statistical Analysis Plan (SAP) will be written with detailed description of all statistical analysis.

### **6. AMENDMENTS TO THE CLINICAL INVESTIGATION PLAN**

No change in the clinical investigation procedure will be implemented without the mutual agreement of the Principal Investigator and Mölnlycke.

An amendment to the Clinical Investigation Plan may require notification or approval from an EC/IRB and, in many countries, also the RA before implementation. Local requirements must be followed.

Mölnlycke will distribute Clinical Investigation Plan amendments to the Principal Investigator who is responsible for the distribution of these documents to the EC/IRB and staff concerned at his/her site. The distribution of these documents to the RA will be handled according to local practice.

### **7. DEVIATIONS FROM THE CLINICAL INVESTIGATION PLAN**

A deviation is a failure to follow, intentionally or unintentionally, the requirements of the Clinical Investigation Plan. Every effort should be made to comply with the requirements of the Clinical Investigation Plan and the Principal Investigator is not allowed to deviate from the plan. Furthermore, the use of waivers from the Clinical Investigation Plan is prohibited.

As required by national regulations, or guidelines, requests for deviations and reports of deviations will be provided to the EC/IRB if the deviation affects subject's rights, safety or well-being, or the scientific integrity of the clinical investigation.

Under emergency circumstances deviations from the Clinical Investigation Plan may proceed without prior approval by Mölnlycke and the EC/IRB if the rights, safety and well-being of human subjects need to be protected. Such deviations will be documented and reported to the Mölnlycke and EC/IRB as soon as possible in accordance with national regulations.

When the Site Monitor or Mölnlycke identifies that the Principal Investigator is out of compliance, this will be communicated to the Principal Investigator in writing, with a request to correct the source of the deviation immediately. Corrective action(s) will be implemented to avoid repeated non-compliance, which will usually include re-training and may include terminating the clinical investigation at the site.

Mölnlycke is responsible for analysing deviations and assessing their significance. Corrective action will be implemented to avoid repeated deviations, which may include suspending the clinical investigation, and/or disqualifying the Principal Investigator.

## 8. STATEMENTS OF COMPLIANCE

### 8.1 Ethics

#### 8.1.1 Ethics review

The final Clinical Investigation Plan, including the final version of the Subject Information and Consent Form, must be approved or given a favourable opinion in writing by an EC/IRB before enrolment of any subject into the clinical investigation. The Principal Investigator is responsible for informing the EC/IRB of any amendment to the Clinical Investigation Plan as per local requirements.

Any additional requirements imposed by the EC/IRB or RA must be followed.

#### 8.1.2 Ethical Conduct of the Investigation

This clinical investigation will be performed in accordance with the ethical principles that have their origin in the most recent version of the Declaration of Helsinki, and applicable regulation.

#### 8.1.3 Subject Information and Consent Form

The Principal Investigator must ensure that the subject is given full and adequate oral and written information about the nature, purpose, possible risks and benefits of the clinical investigation and must verify that the subject has understood the information. Subjects must also be notified that they are free to discontinue participation in the investigation at any time. The withdrawal of the informed consent must not affect the activities already carried out and the use of data obtained based on informed consent before its withdrawal. The subject must be given the opportunity to ask questions and adequate time for consideration prior to providing their consent to take part in the study. The subject's signed informed consent has to be obtained before conducting any procedure specifically for the investigation. The original signed copy of the Informed Consent Form must be filed by the Principal Investigator. A copy of the Subject Information including a copy of the signed Consent Form should be given to the subject.

A sample of the Master Subject Information and Consent Form is enclosed (Appendix B). If modifications are made to either of these documents according to local requirements, Mölnlycke must approve amended version(s) of the document(s).

If any new important information occurs during the clinical investigation the subject will be informed both orally and in writing.

### 8.2 Regulatory and standards

#### 8.2.1 Regulatory review

If applicable, the final Clinical Investigation Plan, including the final version of the Subject Information and Consent Form, must be approved or given a favourable opinion in writing by a RA before enrolment of any subject into the clinical investigation. Mölnlycke is responsible for informing the RA of any amendment to the Clinical Investigation Plan as per local requirements.

#### 8.2.2 Standards and other

The most recent version of ISO 14155 is followed in addition to national regulations.

#### 8.2.3 Subject Data Protection

The written Subject Information explains that the data will be stored in a computer database, maintaining confidentiality in accordance with national data legislation and that authorised representatives of Mölnlycke and/or a RA and/or EC/IRB, may require direct access to those

parts of the hospital/practice records relevant to the clinical investigation, including medical history, for verification of data. All data computerized by Mölnlycke will be identified by subject number only.

### **8.3 SUBJECT PROTECTION PROCEDURES**

#### **8.3.1 Procedures in Case of Medical Emergency**

The Principal Investigator is responsible for ensuring that procedures and expertise are available to cope with medical emergencies during the clinical investigation.

#### **8.3.2 Insurance**

Mölnlycke Health Care AB has product liability insurance, which also covers devices being investigated in a clinical investigation.

## **9. INVESTIGATION TIMETABLE AND TERMINATION**

The study duration per patients is approximately 22 weeks, i.e. treatment duration of up to 20 weeks and follow up 2 weeks after closure.

Planned investigation start: Q4 2019

Planned inclusion completion: Q3 2022

Planned last subject out: Q4 2022

The clinical investigation could be prematurely discontinued if the dropout rate is higher than 20% and/or the investigation site is unable to fulfil the inclusion period according to the Clinical Investigation Agreement.

## **10. PRINCIPAL INVESTIGATOR(S) AND INVESTIGATION ADMINISTRATIVE STRUCTURE**

Specified in separate list.

## **11. DEFINITIONS AND PROCEDURES FOR REPORTING OF ADVERSE EVENT, ADVERSE DEVICE EFFECT, SERIOUS ADVERSE EVENT, SERIOUS ADVERSE DEVICE EFFECT AND DEVICE DEFICIENCY**

### **DEFINITIONS**

#### Device Deficiency (DD)

Inadequacy of a medical device with respect to its identity, quality, durability, reliability, safety or performance.

Note: Device Deficiencies include malfunctions, use errors, and inadequate labelling.

All Device Deficiencies that might have led to a Serious Adverse Device Effect shall be reported in accordance with Serious Adverse Event reporting procedures, as specified below.

#### Adverse Event (AE)

Any untoward medical occurrence, unintended disease or injury, or untoward clinical signs (including abnormal laboratory findings) in subjects, users or other persons, whether or not related to the investigational medical device.

Note:

- This definition includes events related to the investigational medical device or the comparator.
- This definition includes events related to the procedures involved.
- For users or other persons, this definition is restricted to events related to investigational medical devices.

#### Adverse Device Effect (ADE)

Adverse Event related to the use of an investigational medical device

Note:

- a) This definition includes adverse events resulting from insufficient or inadequate instructions for use, deployment, implantation, or operation, or any malfunction of the investigational medical device.
- b) This definition includes any event resulting from use error or from intentional misuse of the investigational medical device.

#### Serious Adverse Event (SAE)

Means any adverse event that led to any of the following:

- a) death,
- b) serious deterioration in the health of the subject, that resulted in any of the following:
  - 1) a life-threatening illness or injury, or
  - 2) a permanent impairment of a body structure or a body function, or
  - 3) hospitalization or prolongation of patient hospitalization, or
  - 4) medical or surgical intervention to prevent life-threatening illness or injury or permanent impairment to a body structure or a body function, or
  - 5) chronic disease
- c) foetal distress, foetal death or a congenital physical or mental impairment or birth defect.

Note: Planned hospitalization for a pre-existing condition, or a procedure required by the Clinical Investigation Plan, without serious deterioration in health, is not considered a serious adverse event.

#### Serious Adverse Device Effect (SADE)

Adverse Device Effect that has resulted in any of the consequences characteristic of a Serious Adverse Event.

#### **PROCEDURES FOR SAE AND/OR SADE REPORTING OR REPORTING OF DD THAT COULD HAVE LED TO A SADE**

The investigator is responsible for the reporting of AEs, ADEs; SAEs, SADEs and DD that occur in the control group in accordance with local requirements to authorities and if applicable manufacturers of these products.

---

**Investigation Code** **Granulox01** **Final Version** **Approval date** **2019-10-24**

---

The Principal Investigator must inform Mölnlycke, within 1 calendar day of awareness of the event. When a SAE/SADE has been entered into the eCRF by the Principal Investigator/authorised site staff, the eCRF system will automatically generate a report to: [Clinical Investigations Event [contact]](mailto:[contact]).

In case of problem with the eCRF, a paper-based version of the SAE/SADE report form (available in the Investigator Site File) shall be used and sent by email to: [Clinical Investigations Event [contact]](mailto:[contact]).

All SAEs/SADEs that occur during the Clinical Investigation shall be reported, whether or not they are considered causally related to the investigational device.

Device Deficiencies that might have led to SADE if either a) suitable action had not been taken, b) if intervention had not been made, or c) if circumstances had been less fortunate must be reported as a SADE.

The Principal Investigator is responsible for informing the EC/IRB and/or the RA of the SAE/SADE as per local requirements.

## PROCEDURES FOR DD REPORTING

All DD shall be reported to Mölnlycke as soon as possible, without unjustified delay. If the DD might have led to a SADE the reporting requirements for SADE described above must be followed. DDs can be either subject related or non-subject related depending on if the investigational device was used by a subject or not. Separate forms are used for subject related and non-subject related DDs.

When a subject related DD has been entered into the eCRF by the Principal Investigator/authorised site staff, the eCRF system will automatically generate a report to: [Clinical Investigations Event [contact]](mailto:[contact])

Non-subject related DDs are reported using the paper-based report form located in the Investigator Site File. The completed form shall be sent by email to: [Clinical Investigations Event [contact]](mailto:[contact])

## PROCEDURES FOR ADE REPORTING

All ADE shall be reported by the Principal Investigator to Mölnlycke as soon as possible without unjustified delay. When an ADE has been entered into the eCRF by the Principal Investigator/authorised site staff, the eCRF system will automatically generate a report to: [Clinical Investigations Event [contact]](mailto:[contact])

This includes also ADEs occurring in the comparator arm.

## CAUSALITY ASSESSMENT

The relationship between the use of the investigational device and the occurrence of each AE/SAE shall be assessed by the Principal Investigator and Mölnlycke and classified as device related or not related to the device.

## Report by Mölnlycke Health Care to Regulatory Authorities

Mölnlycke will report to RA where the clinical investigation has commenced in accordance with the local requirements for market authorised medical devices.

## 12. PUBLICATION POLICY

The clinical investigation will be registered in a publicly accessible database before recruitment of the first subject.

A final Clinical Investigation Report (CIR) of the investigation will be completed, even if the clinical investigation is prematurely terminated. The CIR will be prepared by Mölnlycke in accordance with the guideline presented in Annex D of ISO 14155.

All publications and presentations must be based upon the CIR.

All information supplied by Mölnlycke in connection with this investigation will remain the sole property of Mölnlycke and is to be considered confidential information. No confidential information will be disclosed to other parties not involved in this clinical study without obtaining prior written consent from Mölnlycke. Confidential information associated with this study will not be used except in the performance of this investigation.

Mölnlycke may choose to publish or present data from this clinical investigation. If a Principal Investigator is offered first authorship, he/she will be asked to comment and approve the publication. Mölnlycke has the right to use the results of this study for registration, internal presentation, and for promotion.

## LIST OF ABBREVIATIONS

Abbreviation	Definition
ADE	Adverse Device Effect
AE	Adverse Event
CCC	Confirmed Complete wound Closure
CGI	Clinical Global Impression
CIP	Clinical Investigation Plan
CP	Conditional Power
CRF	Case Report Form
CVI	Chronic Venous Insufficiency
DD	Device Deficiency
EC	Ethics Committee
EOCR	Estimated Overall Closure Rate
EQ-5D-5L	EuroQol.org - 5 dimensions - 5 level instrument to describe and value health
FAS	Full Analysis Set
FCS	Full Conditional Specification
HRQoL	Health-Related Quality of Life
IARC	Interim Analysis Review Committee
IRB	Institutional Review Board
NRS	Numeric Rating Scale
PCC	Possible Complete wound Closure
PP	Per Protocol
PROs	Patient Reported Outcomes
PUSH	Pressure Ulcer Scale for Healing
RA	Regulatory Authority
SAE	Serious Adverse Event
SADE	Serious Adverse Device Effect
WAR	Wound Area Regression
50WAR	50% Wound Area Regression

Statistical Analysis Plan

Protocol:  
**Granulox01**

Protocol No:

Version:  
**D1.0** Page 5 of 23

90WAR	90% Wound Area Regression
VLU	Venous Leg Ulcer
QoL	Quality of Life

## 1 STUDY DETAILS

### 1.1 Study Objectives

#### 1.1.1 Primary Objective

The primary objective of this study is to compare wound healing of chronic VLUs managed using standard of care, with or without added Granulox®, at up to 20 weeks post therapy initiation. The main efficacy criteria is Confirmed Complete wound Closure (CCC).

#### 1.1.2 Secondary Objectives

### 1.2 Study Design

This is a N = 254 patient, European, multi-centre, assessor blinded, 2-arm, randomised controlled study. The study will include multiple European countries (e.g. France, Germany, UK, Poland, Hungary, Croatia and Czech Republic), with approximately 2-7 clinics per country.

The study will run with a two-phase set-up, including a 14 days run-in period and an up to 20 weeks treatment period starting with randomization and allocation of treatment.

#### 1.2.1 Procedures and Assessments

This study starts with a 14 days run-in period to verify two of the required inclusion criteria, i.e. that the wound area does not decrease more than 30% during the run-in period and compliance to compression therapy part of standard of care.

After the 14-days run-in period during which time patients will receive standard of care, (D-14 to D0) patients meeting the selection criteria will be randomly allocated (on D0) to experimental (i.e. standard of care plus Granulox®) or control (i.e. standard of care only) groups. Randomization will be stratified on country, wound duration (<5 months;  $\geq$ 5 months), and wound area after run-in period ( $<10$ ;  $\geq 10$  cm $^2$ ), to ensure equal distribution of test and control in these sub-groups. This, as wound duration and wound area may significantly impact outcomes, and as minor variations in standard of care between study sites may still be present in spite of the measures taken to ensure standardization.

Each patient will be followed to wound closure, or up to 20 weeks (whichever occurs first), with scheduled clinical visits at 1 week (W1), 4 weeks (W4), 8 weeks (W8), 12 weeks (W12), 16 weeks (W16), and 20 weeks (W20). Additional visits are allowed in between the per-

Protocol: Granulox01	Protocol No:
	Version: D1.0

protocol scheduled visits. If suspected wound closure occurs at any point during the study, a final assessment visit will be scheduled 15 days ( $\pm 3$  days) subsequent to the suspected wound closure observation to verify CCC. If wound closure is confirmed, the study is completed for this patient. If wound closure is not confirmed, the patient should continue to be followed according to the schedule of assessments.

In between clinical visits, wound management will follow standard of care. Home visits will be performed by study nurses who are responsible for changing dressing, reapplying Granulox® (for patients randomized to the treatment group only), and reapplying compression therapy. Home visits frequency will follow local practice requirements but must take place at least every 3rd day until epithelialization is complete. The study nurse will record information in the patient-specific diary. If considered necessary, nurses can ask for an additional patient visit to the investigating centre. This is mandatory at suspected complete wound closure.

[figure not shown]
If at any time, a wound graft is required (it usually requires at 24-48 hours hospitalization), study will not be considered as completed and patients will still be followed according to the schedule of assessments (even if experimental treatment is no longer applied) up to CCC occurrence or up to W20 (whichever occurs first).

The study will be stopped before W20 for a given patient in the event of:

- Consent withdrawal
- Impossibility to follow the patient (i.e. lost to follow-up)
- Hospitalization of more than 48h for any reason other than wound graft
- Death
- Reach of endpoint and study completion, i.e. CCC.

In any other cases, including the cessation of experimental treatment for any reason, patient will continue study visits as per schedule of assessment. See details on analyses sets in Section 1.5 "Definition of Study Populations".

## 1.2.2 Flow Chart

Statistical Analysis Plan	
Protocol: Granulox01	Protocol No: 
Version: D1.0	Page 9 of 23

### 1.2.3 Schedule of Assessment

Site visits	Run-in Visit	Home care	Visit 1	Home care	Visit 2	Home care	Visit3	Home care	Visit4	Home care	Visit5	Home care	Visit6	Home care	Visit7	Home care	Final Visit a	Extra visit
Time frames	D-14	D-14-D0	D0	(Day 3)	W1	Every 3 rd day (Day 7 ±1 day)	W4	Every 3 rd day (Day 28 ±3 days)	W8	Every 3 rd day (Day 56 ±3 days)	W12	Every 3 rd day (Day 84 ±3 days)	W16	Every 3 rd day (Day 112 ±3 days)	W20	(Day 140 ±3 days)		
Eligibility criteria	X	X																
Randomization			X															
Demography and background data				X														
Medical and surgical history (including VLU)					X													
Wound picture and status (Tissue Analytics)	X				X			X		X			X		X		X	
PUSH score					X			X		X			X		X		X	
PCC					X			X		X			X		X		X	
Clinical Global Impression (CGI) b																	X	
Patient diary, completed by nurse (e.g. wound care consumables, frequency of dressing change, acceptability of therapy, easy of therapy)			X	X	X		X		X		X		X		X			
Review of patient diary and assessment of compliance			X		X		X		X		X		X		X		X	
EQ-5D-5L and Wound-QoL c			X										X		X		X	

Statistical Analysis Plan	
Protocol: Granulox01	Protocol No.: 
Version: D1.0	Page 10 of 23

Site visits	Run-in Visit	Home care	Visit 1	Home care	Visit 2	Home care	Visit 3	Home care	Visit 4	Home care	Visit 5	Home care	Visit 6	Home care	Visit 7	Home care	Final Visit a)	Extra visit
Time frames	D-14	D-14-D0	D0	(Day 3)	W1	Every 3 rd day (Day 7 ±1 day)	W4	Every 3 rd day (Day 28 ±3 days)	W8	Every 3 rd day (Day 56 ±3 days)	W12	Every 3 rd day (Day 84 ±3 days)	W16	Every 3 rd day (Day 112 ±3 days)	Every 3 rd day (Day 140 ±3 days)	W20 (Day 140 ±3 days)		
NRS (Pain) a)																		
Adverse events e)																		
Medications																		
Reason(s) study arrest																		

a) To be completed in any case (premature arrest, OCC)  
 b) To be completed after patient's study termination and based on patient-series of wound pictures.  
 c) EQ-5D-5L (EuroQoL health status) and Wound-QoL (Quality of Life)  
 d) NRS (Numerical Rating Scale) including pain and pain intensity  
 e) Safety monitoring including reporting of adverse events, serious adverse events, adverse device effects, serious adverse device effects, and device deficiencies.

[figure not shown]
### 1.3 Treatment Groups

The Granulox group will use the same standard of care as the control group but with Granulox. Granulox is a topical haemoglobin spray, which is designed to transport oxygen to the wound size.

The Control group will use the same defined standard of care as the treatment group.

## 1.4 Sample Size

### 1.4.1 Sample size calculation

#### Sample Size Re-estimation

The study will have an adaptive design approach[1] where a pre-defined re-estimation of the sample size will be done after completion of approximately 110 patients. For this purpose, an independent interim analysis review committee (IARC) will be appointed, consisting of at least one person with medical knowledge experience and one experienced statistician.

After approximately 110 patients have completed the study, the IARC will perform an unblinded interim analysis on the primary efficacy variable CCC incidence for the purpose to calculate the conditional power (CP).

Based on the outcome of the CP, the IARC will form a recommendation to either terminate the study, continue the study unchanged, or increase the sample size, according to the following guidelines:

- If  $CP \leq 30\%$ , then terminate the study for futility.
- If  $30\% < CP\% < 80\%$ , then adjust the sample size so that  $CP = 80\%$ . The sample size adjustment will not exceed the maximum of 600 subjects.
- If  $CP\% \geq 80\%$ , then do not adjust the sample size.

Only the recommended sample size adjustment (i.e. no result) will be communicated to the steering group of the study.

This procedure is detailed in [2] and guarantees type I error control.

## 1.5 Definition of Study Populations

**Full Analysis Set (FAS):** All randomized patients with at least one ordinary follow-up visit will be included in the FAS. The final decisions regarding the FAS population will be taken at the Clean File meeting before database lock.

**Per-Protocol (PP) Population:** All patients in FAS with no significant protocol violations will be included in the PP population. The final decisions regarding the PP population will be taken at the Clean File meeting before database lock.

**Safety Population:** All enrolled subjects who received at least application of randomized investigational product (IP) will be included in the safety population.

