## LIST OF ABBREVIATIONS

ADE	Adverse Device Effect
AE	Adverse Event
CCC	Confirmed Complete wound Closure
CIP	Clinical Investigation Plan
CP	Conditional Power
CRF	Case Report Form
CVI	Chronic Venous Insufficiency
DD	Device Deficiency
EC	Ethics Committee
EQ-5D-5L	EuroQol.org - 5 dimensions - 5 level instrument to describe and value health
FAS	Full Analysis Set
HRQoL	Health-Related Quality of Life
IARC	Interim analysis review committee
IRB	Institutional Review Board
NRS	Numerical Rating Scale
PCC	Possible Complete wound Closure
PP	Per Protocol
PRO	Patient Reported Outcome
PUSH	Pressure Ulcer Scale for Healing
RA	Regulatory Authority
SAE	Serious Adverse Event
SADE	Serious Adverse Device Effect
WAR	Wound Area Regression
50WAR	50% Wound Area Regression

---

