### **3.5 Investigational Device**

#### **3.5.1 Summary description of the Investigational Device(s) and Comparator(s)**

##### **3.5.1.1 Investigational Device**

The investigational device is Granulox®, a topical haemoglobin spray, which is designed to transport oxygen to the wound site. Granulox® is intended to increase oxygen supply to the wound. Granulox is a CE marked medical device manufactured by HÄLSA Pharma GmbH (report number: 12911FS06F). It is an innovative product for the treatment of chronic wounds, such as venous leg ulcer, arterial leg ulcer, mixed leg ulcer, diabetic foot ulcers, secondary healing of surgical wounds and pressure sores. Granulox can also be used on sloughy and infected wounds.

The mode of action is that once Granulox® is sprayed, the haemoglobin starts to bind oxygen from the atmosphere and the process of oxygen transportation begins. Oxygen promotes the formation of new blood vessels and subsequently the growth of new skin. Granulox provides the wound with the required oxygen by means of diffusion. The active substance haemoglobin supplies the base of the wound with external oxygen. The improved oxygen supply to the base of the wound supports wound healing.

Granulox® should not be used simultaneously with topical medicines for your wound, such as application of local antibiotics, as interactions have not yet been studied sufficiently. Disinfectants are known to impair the efficacy of Granulox®. Therefore, after application of a disinfectant, the area must be subsequently flushed thoroughly with a physiological solution. Thorough flushing with a physiological solution is necessary after use of proteolytic (enzymatic) debridement.

In this study, Granulox® will be used as intended, in combination with an appropriate foam or wound contact layer wound dressing and in addition to defined standard care.

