### **3.5.1.2 Comparator**

The control group will use the same defined standard of care as the treatment group (see section 3.5.1.1) but without Granulox®.

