### **3.3 Patient Disposition and Data Sets Analysed**

The number of subjects included in each of the FAS, PP and safety populations will be summarized for each treatment group and overall. The number and percentage of subjects enrolled, randomized and treated will be presented. Subjects who completed the study and subjects who withdrew from study prematurely will also be presented with a breakdown of the reasons for withdrawal by treatment group for the FAS, PP and safety populations.

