### 3.8.2 Secondary Efficacy Analyses

### 3.8.3 Analyses of Exploratory Efficacy variables.

**3.8.4 Sub-group analyses****3.8.5 Exploratory Interaction analyses between treatment and baseline variables****3.9 Safety Analyses****3.9.1 Adverse Events**

All safety variables will be summarized and analysed descriptively by treatment group on the safety population.

The number of subjects reporting one or more AE/ADE/SAE/SADE/DD will be summarised by treatment group using frequency counts. If very few AE/ADE/SAE/SADE/DD these will only be listed.

The incidence (%) of AE/ADE/SAE/SADE/DD reported during the investigation will be summarised in an overview table and by treatment group.

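### Does defining the safety population by receipt of investigational product leave the control arm out of the safety tables?

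*SAP*

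**What the plan says.** Protocol 5.2.1 and SAP 1.5 carry one identical sentence: "All enrolled subjects who received at least application of randomized investigational product (IP) will be included in the safety population". Protocol 3.5.1.1 states "The investigational device is Granulox" and describes the defined standard of care under the same heading. Protocol 3.5.1.2 says of the comparator: "The control group will use the same defined standard of care as the treatment group (see section 3.5.1.1) but without Granulox". SAP 1.3 gives the mirror image: "The Granulox group will use the same standard of care as the control group but with Granulox".

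The safety population is used in two places. SAP 3.3 says "The number of subjects included in each of the FAS, PP and safety populations will be summarized for each treatment group and overall", and asks for a "breakdown of the reasons for withdrawal by treatment group for the FAS, PP and safety populations". SAP 3.9.1 says "All safety variables will be summarized and analysed descriptively by treatment group on the safety population", followed by counts of subjects with events and incidence percentages, both by group.

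**The concern.** The entry rule turns on a term that the documents do not explain. IP appears in neither abbreviation list, and the nearest defined phrase is the investigational device, which is Granulox alone. If a programmer treats the two as the same thing, no control patient has received the product and none enters the set. The sentence has also lost the number of applications required.

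Safety of an add-on device is judged against its control arm. An empty control column would remove that comparison and contradict the by-group tables that the SAP itself orders. Because both documents use the same sentence, neither corrects the other.

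**Working it through.** There is no planned figure to reproduce. The check is whether the plan, read as a whole, leaves real doubt about who is in the set.

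**1. Is the term undefined?** Yes, in the visible text. The Protocol abbreviation list has 24 + 3 = 27 entries and the SAP list 27 + 3 = 30, counting the entries that run over the page. IP is in neither.

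**2. What would each reading give?** Inputs: N = 254 (Protocol 3.1, SAP 1.2) and the maximum of 600 (Protocol 5.1.2, SAP 1.4.1). Assumptions: 1:1 allocation, and every patient treated after randomisation.

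| Reading of IP | N = 254: Granulox / control | N = 600: Granulox / control |
|---|---|---|
| Granulox only | 254/2 = 127 / 0 | 600/2 = 300 / 0 |
| Treatment allocated by randomisation | 127 / 127 | 300 / 300 |

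**3. Which reading fits the other sections?**

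- *The sentence itself.* The product is qualified by the word randomized. If it meant Granulox alone, that word would add little. It reads naturally as the treatment to which the patient was randomised. It also shuts out standard of care given in the run-in, before anything has been allocated, even though the sentence starts from enrolled subjects.
- *SAP 3.3.* The set is counted in each treatment group and withdrawal reasons are split by group. With no controls, both displays would be pointless for this set.
- *SAP 3.9.1.* Events are counted and incidence is given by group on this set. Again two groups are needed.
- *SAP 2.3.1.* The stated purpose is safety of the study treatments, in the plural.
- *Protocol section 11.* An adverse device effect is defined by use of an investigational device, yet the reporting rules cover adverse device effects in the comparator arm, and serious device effects and device deficiencies in the control group. The protocol therefore does not confine its investigational vocabulary to Granulox.
- *Against.* The adverse event definition in section 11 does name device and comparator separately, and Protocol 3.5.1.2 has its own Comparator heading. Usage is mixed.

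So the zero-control reading requires replacing one phrase (investigational product) with another (investigational device), and it then fails against SAP 3.3 and 3.9.1. The allocated-treatment reading fits all the sections that use the set.

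**4. What depends on it?** SAP 3.1 puts all analyses of primary and secondary variables on the FAS, with the PP population as complement. The visible uses of the safety set are descriptive: two disposition displays in SAP 3.3 and two event summaries in SAP 3.9.1. The SAP's list of tables is not legible in the public copy, so this is a minimum count.

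**5. The missing number.** The only sensible completion of the phrase is one application, which is the lowest exposure that can be counted.

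**The case for a change.** The best case for a correction is that an analysis set should be fixed by its own words and not by inference from the tables. The vocabulary in Protocol 3.5 does point to Granulox as the only investigational item, the repair would be one sentence in each document, and control-arm safety is the reference for the whole safety description. It is also true that the clean-file meeting is named for decisions on the FAS and PP populations and not for the safety set.

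Part of this stands. The sentence is loosely drafted, and a patient allocated to Granulox who received only standard of care is not clearly placed. No rule is visible for grouping by treatment allocated or treatment received.

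The rest carries little weight. An empty control column would show itself in the first draft of any by-group table. Protocol 4.3 requires decisions on the evaluability of each subject's data to be made and documented before database lock, which covers the odd case in practice. Rewording carries its own risk: a definition tied to receipt of the full allocated regimen could drop the unsprayed Granulox patient while admitting a control with the same exposure. Control-arm events are collected whichever words are used, so no data are at risk.

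**Conclusion.** The concern does not hold as a fault in the plan. The abbreviation is undefined and a numeral has dropped out; both are clerical. The tables, the reporting rules and the sentence's own qualifier all point to a set containing both arms, and an analyst following the plan will build it that way: about 127 and 127 at N = 254, on the assumption of 1:1 allocation with everyone treated.

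No efficacy estimate, power or type I error figure depends on the point, and no descriptive safety result is expected to change. The conclusion rests on the visible text. Several SAP sections are blank in the public copy, and a definition there could only make the matter clearer.
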